	
identified, the date described as the last date of the treatment should be employed.
 
[3] When there is no description in the section for the last date of the third or subsequent treatment or there is a check mark in “Ongoing” box so that the last date of the treatment cannot be identified, following rules are applied.
 
 
● When the patients are included in the last period in the volume: The date should be complemented by the last follow-up date for relevant volume or a date obtained by subtracting 1 day from start date of the subsequent treatment, which is earlier.
 
● When the patients are included in not last period in the volume: The date should be complemented by a date obtained by subtracting 1 day from the start date of the subsequent treatment with this drug.
 
 
The last follow-up date should be defined as follows:
 
 
• The initial volume: Start date of the treatment with this drug + 364 days
 
• The second volume: Start date of the treatment with this drug + 728 days
 
• The second volume: Start date of the treatment with this drug + 1092 days
 
 
[4] When there is description in the section for the last date of the third or subsequent treatment but the date is incomplete so that the last date of the treatment cannot be identified, following rules are applied.
 
 
● When the date include year and month, but date is unknown: The date should be complemented by the last date of relevant month.
 
● When the date include year, but month and date is unknown: The date should be complemented by the last date in the last month of relevant year. In addition, when records in the subsequent treatment are created and the start date of the subsequent treatment is earlier than the complemented last date in the last month of the relevant year, the last date of the treatment should be complemented by the date obtained by subtracting 1 day from the start date of the subsequent treatment.
 
 
However, if description in the last date of the treatment in the records for which last date of the treatment was complemented according to above rules and there is a check mark in “Ongoing” box, following rules are applied:
 
 
● When the described last date of the treatment is later than the last date complemented according to above rules, the date complemented should be employed as the last date of the final treatment of this drug.
 
● When the described last date of the treatment is earlier than the last date complemented according to above rules, the date described should be employed as the last
 

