Patients who discontinued the administration	If the last date of the final administration of this drug corresponds to following conditions, the patients are deemed to be those who discontinued the administration.

Name of data	Derivation and calculation method
	
Patients who started to receive this drug by August 15, 2013: The start date of the initial administration + less than 1064 days
 
Patients who started to receive this drug between August 16, 2013 and August 15, 2014: The start date of the initial administration + less than 700 days
 
Patients who started to receive this drug between August 16, 2014 and August 15, 2015: The start date of the initial administration + less than 350 days

Presence or absence of reasons for discontinuation	
If patients correspond to those who discontinued the administration and there is at least one check mark in any “Reasons for discontinuation” boxes in “Discontinuation of the survey” section in the survey sheet, the patients are deemed as having reasons for discontinuation and if no description is found in the “Reasons for discontinuation” box in the survey sheet of patients defined as those who discontinued the administration, such patients are defined as patients whose reason for discontinuation is “unknown or not described reason”.

Patients who continue to participate in the survey	
Patients who do not correspond to those who discontinued administration are deemed as patients who continue to participate in the survey.

Presence or absence of complications	
If there is a check mark in a box for complication in “patient information” in survey sheet, such patients are deemed to have complication, and if a column for “presence or absence of complications” is not completed and cannot be assessed, whether patients have complication or not is deemed as unknown or not described, and in any other situations, patients are deemed to have no complication.

Presence or absence of medical history	
If there is a check mark in a box for medical history in “patient information” in the survey sheet, patients deemed to have medical history, and a column for “presence or absence of medical history” is not completed and cannot be assessed, whether patients have medical history or not is deemed as unknown or not described, and in any other situations, patients are deemed to have no medical history.

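### A recorded discontinuation is overridden by an imputed end date when that date is blank in the patient's final volume, or year-only and completed past the cut-off

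*SAP*

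**What the plan says.** SAP section 10.1 builds the last date of the final treatment in steps.

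- First and second treatments: the end date is set to the start date of that record.
- Blank date: the rule opens "When there is no description in the section for the last date of the third or subsequent treatment" and treats this case like a ticked 'Ongoing' box. For the last period in a volume, "The date should be complemented by the last follow-up date for relevant volume", or by the day before the next treatment starts, whichever is earlier.
- Last follow-up dates: start + 364 days in the first volume. The next line reads "The second volume: Start date of the treatment with this drug + 728 days", and the one below it has "The second volume: Start date of the treatment with this drug + 1092 days". The third line repeats the label of the second; I read it as the third volume.
- Year-only date: "The date should be complemented by the last date in the last month of relevant year". Any result later than the last follow-up date is cut back to it.

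The same section defines a patient as having discontinued when this completed date falls before start + 350 days (52-week cohort), + 700 (104-week) or + 1064 (156-week). Then: "Patients who do not correspond to those who discontinued administration are deemed as patients who continue to participate in the survey". Reasons are conditional on that status: "If patients correspond to those who discontinued the administration and there is at least one check mark in any" reason box in the 'Discontinuation of the survey' section, the patient has a reason for discontinuation. No rule lets a ticked reason change the status.

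**The concern.** A tick in the discontinuation section is recorded information; the completed date is an assumption. Where they disagree, the plan follows the assumption and discards the record. Section 9.1 makes non-imputation the default, so this is a chosen exception.

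Table 1.7 is the direct casualty: it counts discontinued patients and their reasons, and not visiting is one of the listed reasons. The completed date also feeds the exposure figures in Table 1.6. The derived status decides whether the safety window in section 2 ends at last date + 28 days or at start + 392, 756 or 1120 days, and how far into the onset periods of Table 2.7 a patient is counted.

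**Working it through.** **Reproducing the plan's offsets.** 52 × 7 = 364, 104 × 7 = 728, 156 × 7 = 1092. The cut-offs are 350 / 7 = 50, 700 / 7 = 100 and 1064 / 7 = 152 weeks.

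**Blank end date, third or later treatment, no later record.**

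| Cohort | Volume with the blank | Completed date | Cut-off | Derived status |
|---|---|---|---|---|
| 52-week | first (final) | start + 364 | 350 | continuing |
| 104-week | first | start + 364 | 700 | discontinued |
| 104-week | second (final) | start + 728 | 700 | continuing |
| 156-week | first | start + 364 | 1064 | discontinued |
| 156-week | second | start + 728 | 1064 | discontinued |
| 156-week | third (final) | start + 1092 | 1064 | continuing |

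A blank in the final volume always gives continuing. In an earlier volume the status is right, though the end date is still pushed to the end of that volume. A stop after the first or second treatment takes the record's start date, so it is correctly discontinued.

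**Year-only date.** The patient is classed as continuing when min(31 December − start, last follow-up offset) reaches the cut-off. Take an entry of 2015 in the 52-week cohort (starts 16 August 2014 to 15 August 2015). From 15 January 2015 to 31 December 2015 is exactly 350 days, which is not below 350; from 16 January it is 349. Misclassified start dates: 16 + 30 + 31 + 30 + 31 + 15 = 153 of 365 (42%). The other 212 stay discontinued. An entry of 2014 in this cohort is always discontinued: the longest span, from 16 August 2014, is 137 days.

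I also enumerated every start date against every stop from day 28 to the day before the cut-off. This assumes uniform stops and, for the 156-week cohort, a first start on 16 May 2013. A year-only date then gives continuing in about 56%, 27% and 14% of start/stop pairs (52-, 104- and 156-week cohorts). A date with year and month does so in only 1.4% to 4.6%.

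**One affected patient (hypothetical).** 52-week cohort, maintenance record from start + 28, true stop at week 12 (start + 84), reason ticked, end date blank, 40 mg every 2 weeks as tabulated:

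- Administrations on that record by the SAP's formula: (364 − 28) / 14 = 24 instead of (84 − 28) / 14 = 4. That is 20 extra, or 20 × 40 = 800 mg.
- Exposure: 364 − 84 = 280 extra days.
- Safety window: ends at start + 392 instead of 84 + 28 = start + 112.
- Table 2.7: the patient should leave within the 85–168 day period, but is also counted in 169–364 and 365–728.

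**Effect on the discontinuation count (assumption, not from the SAP).** With 40 true discontinuers per 100 patients, all with the section completed, and 5%, 10% or 20% of them blank in the final volume, the plan reports 38, 36 or 32 discontinued.

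**The case against.** Several limits stand. A reader might infer that any blank or year-only date turns a discontinued patient into a completer. The rules do not do that: blanks in a non-final volume, stops after the first or second treatment, and most start dates even in the 2015 example keep the right status.

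A reader might also infer that the reported adverse-reaction incidence is lowered throughout. The general rule in section 10.2 divides by all patients in the safety analysis, whatever their discontinuation status. The longer window can only leave the counts in Tables 2.1, 2.17 and 2.18 unchanged or add recorded events. Dilution is confined to the later periods of Table 2.7.

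Tables 2.19.1 and 2.19.2 select patients who left the survey for insufficient effect without citing the derived flag, so that selection may come straight from the sheet. Patients whose dosing was adjusted for insufficient effect enter by a separate route.

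Frequency is unknown. It is plausible that patients who stop attending have the least certain last injection date, but the SAP gives no evidence for it, and data queries before sheets are fixed may remove many such cases.

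Finally, leaving the survey is not the same as stopping the drug, so a survey tick should not by itself shorten the safety window and drop events. This limits the remedy; it does not defend the present rule, under which no tick can ever correct the status.

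**Conclusion.** The defect holds within stated bounds and should be fixed. From the third treatment on, a patient with a completed discontinuation section is classed as continuing, and the reason is dropped from Table 1.7, in two cases: (a) a blank end date in the last period of the cohort's final volume, always; (b) a year-only end date, when 31 December capped at the last follow-up date reaches the cut-off.

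For these patients exposure in Table 1.6 is lengthened, the safety window runs to the scheduled end, and they sit largely unobserved in later Table 2.7 denominators. Tables 2.19.1 and 2.19.2 are affected only if they use the derived flag. This rests on the literal wording of section 10.1 and on the third follow-up line meaning the third volume. The number of patients affected cannot be known from the SAP.

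**What to change.** In section 10.1, let a completed 'Discontinuation of the survey' section set the discontinued status and keep the reason for Table 1.7, and for Tables 2.19.1 and 2.19.2, whatever the completed date. Keep the date rule for patients without such an entry.

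For patients with such an entry, do not complete a blank or year-only end date to the scheduled end of the volume or year. Bound it by the last dated evidence of drug administration, or treat it as unknown, in Tables 1.6 and 2.7. Adverse event and laboratory dates should not serve as this bound, since they can fall after the last dose.

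Report the number of imputed end dates. Show separately any adverse reactions between the bounded date + 28 days and the scheduled window end, so that no recorded event is lost.

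The cost is SAP wording and reprogramming from survey-sheet data. The downside is a somewhat higher discontinuation rate and possibly slightly understated exposure for a few patients.

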## 10. Data derivation and calculation method

### 10.1. Overall

Name of data	Derivation and calculation method
The number of institutions	When a institution have an identical DCF institution cord in “List of [HUMIRA BD] DCF cords_Company A” and “List of [HUMIRA BD] DCF cords_Company E”, such institution is counted as one institution.
The number of patients per institution	The number of patients should be calculated by institution with the identical DCF institution cord.
The number of patients who continue to participate in clinical study	Patients with box being checked in “Patients who participate in clinical trial of this drug” in a section of administration status in registration sheet are applicable.
Patients in whom adverse events occurred outside the specified safety analysis period	Patients who experienced at least one adverse event that occurred outside the specified safety analysis period.
Patients who are excluded from separate volume	Patient number and volume number that are excluded from analysis should be specified from “[HUMIRA BD] patients included in separate volume.xlsx” to exclude applicable data at the analysis.
Patients in whom infection occurred	When patients have at least one event corresponding to conditions of infection in “20161110_MedDRA18.1 and 19.1 List of primary survey item_PV”, such patients should be applicable.
Patients in whom tuberculosis occurred	When patients have at least one event corresponding to conditions of tuberculosis in “20161110_MedDRA18.1 and 19.1 List of primary survey item_PV”, such patients should be applicable.
Patients in whom malignant tumour occurred	When patients have at least one event corresponding to conditions of malignant tumour in “20161110_MedDRA18.1 and 19.1 List of primary survey item_PV”, such patients should be applicable.
Patients in whom administration reaction occurred	When patients have at least one event corresponding to conditions of administration site reaction in “20161110_MedDRA18.1 and 19.1 List of primary survey item_PV”, such patients should be applicable.
Patients in whom autoimmune disease occurred	When patients have at least one event corresponding to conditions of autoimmune disease in “20161110_MedDRA18.1 and 19.1 List of primary survey item_PV”, such patients should be applicable.

Name of data	Derivation and calculation method

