#### [1] Patients with fixed data by separate volumes

Data included in analysis: Patients for whom a survey sheet data was fixed

Objective of analysis: The number of patients with fixed data by separate volumes is shown.

Analysis items: The number of patients with fixed data for the initial, second, and third volume should be calculated by patients whose survey sheet data was fixed, patients included in safety analysis, and patients included in efficacy analysis.

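### In the 104- and 156-week cohorts, a patient still marked Ongoing in a volume earlier than the scheduled last one is classed as having discontinued the drug

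*SAP*

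**What the plan says.** Section 10.1 of the SAP derives the last treatment date in steps. For a third or later treatment record that has no end date or has Ongoing ticked, and that is in the last period of its volume, the rule is: "The date should be complemented by the last follow-up date for relevant volume". If another treatment follows and the day before it began comes sooner, that day is used instead. For the first volume the limit reads "The initial volume: Start date of the treatment with this drug + 364 days"; the line after it gives "The second volume: Start date of the treatment with this drug + 728 days"; and a third line gives "The second volume: Start date of the treatment with this drug + 1092 days". The last of these is labelled as the second volume again; from the sequence it must be the third. The latest date obtained becomes the patient's last treatment date.

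The next step in 10.1 classes a patient as having discontinued when that date falls short of a cut-off set by the start-date cohort. For the earliest starters (156-week cohort) the cut-off is "The start date of the initial administration + less than 1064 days"; for the 104-week and 52-week cohorts it is 700 and 350 days. Everyone else is deemed to be continuing in the survey. There is no third status.

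Data are handled volume by volume. Section 10.1 allows a single volume of a single patient to be dropped ("Patient number and volume number that are excluded from analysis should be specified" from a separate file), and Table 1.1.1 reports fixed data per volume ("The number of patients with fixed data for the initial, second, and third volume should be calculated").

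**The concern.** The filled-in date depends on which volume is the last one available. The cut-off depends on the cohort's full schedule. Neither the Ongoing tick nor the number of volumes available enters the comparison. When the last available volume is earlier than the scheduled last one, the two limits do not match, and the physician's statement that treatment continues becomes a discontinuation.

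The result confuses incomplete survey data with stopping the drug. It enters the count and rate in Table 1.7. It also enters Table 2.19.2 (patients with insufficient response, split by discontinuation), list 1.16 (which shows Ongoing only for patients classed as continuing) and the list of patients aged 18 or younger, which shows discontinuation and its reason.

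**Working it through.** The SAP states no discontinuation rate or sample size, so there is no figure of its own to reproduce. The check compares the two sets of limits.

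**Inputs (section 10.1).** Volume limits: start + 364, + 728, + 1092 days. Cut-offs: 350 (52-week cohort), 700 (104-week), 1064 (156-week). A patient is discontinued if the last date is below the cut-off. In the last available volume there is no later treatment record, so the volume limit applies and not the day before the next treatment.

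| Cohort | Last available volume | Filled date | Cut-off | Difference | Class |
|---|---|---|---|---|---|
| 52-week | 1 (scheduled last) | 364 | 350 | +14 | continuing |
| 104-week | 2 (scheduled last) | 728 | 700 | +28 | continuing |
| 104-week | 1 | 364 | 700 | −336 | discontinued |
| 156-week | 3 (scheduled last) | 1092 | 1064 | +28 | continuing |
| 156-week | 2 | 728 | 1064 | −336 | discontinued |
| 156-week | 1 | 364 | 1064 | −700 | discontinued |

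Counting the start date as day 1 adds one day to each filled date and changes no class. A missing middle volume does no harm when a later one is available, because the latest date is used.

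**Effect on the rate.** Let d be the true proportion discontinued, and u the share of all analysed patients who fall in one of the three affected rows and are truly still on drug. Reported rate = d + u. The SAP gives neither d nor u, so both are assumed. With d = 30%:

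- u = 0: 30%
- u = 2%: 30 + 2 = 32%
- u = 5%: 30 + 5 = 35%
- u = 10%: 30 + 10 = 40%

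**Other limits that use the flag.** Section 2 ends the safety period of a discontinued patient 28 days after the last date: 364 + 28 = 392 and 728 + 28 = 756. These equal the limits section 2 gives to the 52- and 104-week cohorts. Section 12.3 allows 14 days for overall improvement: 364 + 14 = 378, which is 52 weeks + 14 days. For the second volume, 728 + 14 = 742, against 756 for a continuing 104-week patient, a gap of 14 days.

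**The case against.** The strongest reply is that the number affected is unknown and may be zero. Counts per volume are needed in any case, because the cohorts are designed for one, two or three volumes. The exclusion rule points to a file that is not shown, and that file might only remove volumes beyond a cohort's schedule. This stands: the SAP makes such patients possible but does not show that there are any.

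A second reply is that Table 1.7 concerns leaving the survey, and a patient with no later volume has arguably left it. This stands only in part. Section 10.1 derives the status from the treatment date, names it discontinuation of administration, and defines continuing in the survey as its complement. The two ideas are merged, and the outputs present the result as one status.

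Several stronger readings are tempting but not supported:

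- *Every Ongoing patient is misclassified.* No. With the scheduled last volume available, all three cohorts are classed as continuing, and this rule cannot affect the 52-week cohort.
- *Safety data are lost because the window is cut.* The window ends where the last available volume's own limit would end it (day 392 or 756). Adverse reactions outside the safety period are tabulated separately in Table 2.1.2.
- *Efficacy ratings are lost.* The difference is at most about 14 days, and if the later volume is absent, so are its ratings.
- *All the excess would appear without a stated reason.* A patient with no later volume may still have a reason ticked, such as not visiting.
- *A missing-volume share among continuing patients of the longer cohorts can be applied to the whole survey.* It must first be scaled down for the 52-week cohort. With equal true rates of 30%, an assumed one-third of patients in that cohort and an assumed missing share of 10%, the overall rate is 30 + 10% × 70 × 2/3 = 34.7%, not 37%.

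**Conclusion.** The point holds for the 104- and 156-week cohorts when the last available record is Ongoing (or has no end date and no discontinuation entry) and the last available volume is earlier than the scheduled last one. Three of the six combinations of cohort and last available volume are then classed as discontinued by construction, short of the cut-off by 336 to 700 days. The discontinuation rate in Table 1.7 is too high by the share of analysed patients in that position who are truly still on drug. The size cannot be derived from the SAP: 2 to 10 percentage points is an illustration, and zero is possible. Some of these patients may have stopped later without a record, so the error is that an unknown status is reported as a known one. The matter concerns status and labelling, not the safety or efficacy windows.

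**What to change.** In section 10.1, add a third status, *ongoing at last available volume (follow-up incomplete)*. It would cover a 104- or 156-week patient whose last available record is Ongoing, or has neither an end date nor a discontinuation entry, and whose last available volume is earlier than the cohort's scheduled last volume. Show it as a separate row in Table 1.7, outside the discontinued count. The reader can then see the rate with and without these patients. Carry the status into Table 2.19.2, list 1.16 and the list of patients aged 18 or younger.

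Leave the safety period and the Table 2.7 denominators ending at the last available volume's limit, as they effectively do now. Treating these patients as observed to the end of the cohort schedule would add follow-up that was never collected.

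The cost is a few more lines in the derivations and in those tables. No new data are needed.

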
Name of data	Derivation and calculation method
	
date of the final treatment of this drug.
 
In addition, the last date identified according to above rule is later than the last follow-up date, the last follow-up date should be employed as the last date of the final treatment with this drug.

Days to the last date of the final treatment with this drug	
The last date of the final treatment with this drug - the start date of the initial treatment with this drug + 1

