Patients in whom dose increase was made	
Patients in whom 160 mg/2 weeks was administered as the initial dose, 80 mg/2 weeks as the second dose, 40 mg/2 weeks as the third and subsequent dose, and 160 mg or 80 mg was administered at least once thereafter are applicable.

Administration status (total number of administrations, dose)	
 
The number of administrations 
 
[1] Data should be sorted by the start date of the treatment, separate volume, and the number of the cycle of treatment described in “Administration status of this drug” in that order.
 
[2] Administration intervals should be calculated by administration status.
 
 
 
The administration interval should be 14 days for the initial and second administration.
 
The third and subsequent administration should be given according to following rules.
 
If there is a check mark in “once/2 weeks” box, the administration intervals should be 14 days, and in any other situations, a data should be obtained from “[HUMIRA BD] converted data to be provided for analysis”.
 
[3] The number of administrations by administration status should be calculated.
 
The number of administrations = (The last date of the administration (after complement) - the start date of the administration (after complement))/the administration intervals (days)
 
[4] Result obtained according to [3] is larger than 0 and smaller than 1, the number of administrations should be 1.
 
In addition, that number is 1 or larger, the number of administrations should be obtained by rounding off the decimal point.
 
[5] The number of administrations should be sum total of [4] by patients
 
 
Dose 
 
[1] If the dose of this drug is classified as other, the data should be obtained from “[HUMIRA BD] converted data to be provided for analysis”.
 
[2] The dose by administration status should be calculated.
 
 
 
The dose = The number of administrations × the dose
 
[3] Total dose should be sum total of [2] by patients
 
 
Mean daily dose 
 
Mean dose = Total dose/Total number of administrations
 
 
 
 

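### Month-only treatment end dates are filled to month end without the next-start cap used elsewhere, so dosing records can overlap and inflate the injection count

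*SAP*

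**What the plan says.** SAP Section 10.1, entry on the last date of the final treatment, sets out how missing or incomplete end dates of third and later dosing records are completed.

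- **Blank or ongoing end date, rule [3], record not last in its volume:** "The date should be complemented by a date obtained by subtracting 1 day from the start date of the subsequent treatment with this drug". For the last record in a volume, the earlier of the last follow-up date and the day before the next start is used.
- **Month and year known, rule [4], first bullet:** "The date should be complemented by the last date of relevant month". The bullet ends there.
- **Year only, rule [4], second bullet:** 31 December is filled in. If a later record exists and its "start date of the subsequent treatment is earlier than the complemented last date in the last month of the relevant year", the end is "complemented by the date obtained by subtracting 1 day from the start date of the subsequent treatment".
- **Closing rule:** if the derived date lies beyond follow-up, "the last follow-up date should be employed as the last date of the final treatment with this drug".

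The entry on administration status (total number of administrations, dose) reuses the completed dates. Each record's count is its completed end minus its start, divided by the interval. For a record ticked as once per two weeks, "the administration intervals should be 14 days"; otherwise the interval comes from a converted data file. A result between 0 and 1 becomes 1, and a larger one is rounded off. Then "The number of administrations should be sum total of [4] by patients". Total dose is the sum of count times dose over records, and the mean dose is total dose divided by total number of administrations.

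**The concern.** Among the rules that impute an end date, only the month-only bullet lets that date run past the start of the next record. Because counts are formed record by record and then added, days in the overlap can yield injections under both records.

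The quantities at stake are the number of administrations, the total dose and the mean dose. They feed Table 1.6, the mean dose and duration-of-use items of Table 2.3 (Appendix 3), and the mean daily dose factor in Tables 2.9 and 3.4. Only patients with a further record can be affected. These include patients whose dose or interval was changed, a group the plan reports on separately in Tables 2.19.1 and 2.19.2.

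**Working it through.** The SAP states no figure on this point, so there is none to reproduce. The check has four parts.

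**1. Does another rule close the gap?** The trigger of the year-only cap names the completed date in the last month of the year, so it does not reach the month-only bullet. The later rule that compares a described end date with the completed one requires the Ongoing box to be ticked. The closing rule caps only at the last follow-up date. The counting entry has no overlap check. The gap is open.

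**2. Dated examples (dates assumed).** Record 1 starts 5 Jan 2015, every 14 days, with its end given only as March 2015. The current rule sets the end to 31 Mar: 85/14 = 6.07, so 6 injections.

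| Next record starts | Overlap (days) | Injections before next start | Capped end, nearest integer | Uncapped |
|---|---|---|---|---|
| 2 Mar | 30 | 4 | 55/14 = 3.93 → 4 | 6 |
| 16 Mar | 16 | 5 | 69/14 = 4.93 → 5 | 6 |
| 30 Mar | 2 | 6 | 83/14 = 5.93 → 6 | 6 |

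The excess is two, one or none, depending on where in the month the next record starts.

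**3. How often, under a stated set-up.** Assume that record 1 holds k injections at interval d, that record 2 starts d days after the last of them, and that the month given is the month of the last injection. Let r be the number of days from the last injection to month end.

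- Overlap occurs when r ≥ d.
- Capped count = round((dk − 1)/d) = k, the true number.
- Uncapped count = k − 1 + round(r/d), so the excess is round(r/d) − 1.

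Over the 365 possible last-injection dates of a non-leap year, a month of D days contains D − m dates with r ≥ m. Over 12 months that makes 365 − 12m dates.

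*d = 14 (the SAP's two-weekly interval):*
- Overlap (r ≥ 14): 365 − 168 = 197 dates; 197/365 = 54.0%. Mean overlap 8.7 days, maximum 17.
- Excess of one (r/14 ≥ 1.5, so r ≥ 21): 365 − 252 = 113 dates; 113/197 = 57% of overlaps, or 113/365 = 31% of all such records. Since r is at most 30, the excess never exceeds one.

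*d = 7 (assumed; the SAP lists weekly categories in Table 2.19.2 but does not say how many records are weekly):*
- Overlap (r ≥ 7): 365 − 84 = 281 dates; 281/365 = 77.0%. Mean overlap 12.2 days, maximum 24.
- Excess of at least one (r/7 ≥ 1.5, so r ≥ 11): 365 − 132 = 233 dates; 233/281 = 83% of overlaps. The maximum is round(30/7) − 1 = 3.

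If the month given is instead that of the day before the next start, as in the 2 Mar example, 76% of 14-day overlaps add at least one injection (mean 1.05, maximum 2). At 7 days the share is 86% and the maximum 4.

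**4. Direction of the mean dose.** The extra injections carry the earlier record's dose. As an illustration, take one injection of 160 mg, one of 80 mg, ten of 40 mg and five of 80 mg: 1040/17 = 61.2 mg. One spurious 40 mg injection gives 1080/18 = 60.0 mg. After a dose increase the mean falls; it rises only when the earlier dose is above the patient's mean.

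**The case against.** The strongest reply is that little reaches the outputs. An effect needs a third or later record, an end date known only to the month, and a further record starting by that month end. In the 14-day set-up above, 43% of overlaps leave the count unchanged. The final treatment date takes the latest completed date, so it moves only if the later record ends before the imputed month end. The maximum dose in Appendix 3 is unaffected. The Section 11 bands are wide (500 to 1000 mg for most total-dose bands, 20 mg for most mean-dose bands), so one injection reclassifies only borderline patients. All of this stands, and it is why the point is minor.

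A second reply concerns rounding. If rounding off meant truncation, the capped date would give k − 1, one short in every 14-day overlap, while the uncapped date would be right in 85% of them. This does not rescue the bullet. The plan's own end dates at next start minus 1 day in rule [3] and the year-only bullet would be short in the same way, and Section 9.3 uses rounding off in the ordinary nearest-digit sense. It does show that the rounding should be stated.

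A third reply is that an unguarded cap could override reported data: if the next record starts on or before the first day of the recorded month, the end moves into an earlier month. That stands and is handled in the fix.

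**Conclusion.** The gap is real, and no other rule in the SAP closes it. Followed as written, the month-only bullet can overstate the number of administrations and total dose, and can distort the mean dose in either direction. Per affected record, the excess at 14-day spacing is none or one injection in the set-up above, and at most two if the month refers to the day before the next start. At an assumed weekly spacing it is at most three or four respectively. These figures rest on the assumed start of the next record and on nearest-integer rounding. The number of month-only records is not given, so the total effect cannot be sized.

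A reader might infer that every patient with a regimen change has injections counted twice, or that mean dose is overstated in dose-adjusted patients. The document supports neither. Overlap is conditional and often leaves the rounded count unchanged, and after a dose increase the mean goes down. Nor does the SAP say that a regimen change is the usual reason for a further record.

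**What to change.** Three small edits in SAP Section 10.1:

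1. Add the cap to the month-only bullet of rule [4]: if a subsequent record starts on or before the completed month end, the end date is the next start date minus 1 day. The trigger has to include equality, because a record starting on the month end itself also overlaps. The year-only trigger, which requires an earlier start, could be aligned at the same time.
2. State in step [4] of the administration count that values of 1 or more are rounded to the nearest integer.
3. Query, rather than cap automatically, any record whose successor starts on or before the first day of the recorded end month.

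The cost is a clause or two of text, about one line of code and a short query listing. No new data collection is needed. This is a date-derivation rule only and implies nothing about dosing.
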